7 DISCONTINUATION OF IMP AND PARTICIPANT DISCONTINUATION/WITHDRAWAL

7.1 Discontinuation of IMP

A study participant should be withdrawn from IMP and will be asked to come back for the SFU Visit 17 weeks after the final dose of IMP if any of the following events occur:

1. Study participant develops an illness that, in the opinion of the Investigator, would interfere with his/her continued participation if the risk of continuing participation outweighs the potential benefit.

2. Study participant develops erythrodermic, guttate, or pustular form of PSO.
3. Study participant is noncompliant with the study procedures or medications in the opinion of the Investigator.
4. Study participant uses prohibited concomitant medications (as defined in Section 6.5.2) that may present a risk to the safety of the study participant or the integrity of the study data, in the opinion of the Investigator and/or the Medical Monitor.
5. Study participant has a clinical laboratory value meeting any of the following criteria:
 - Hepatotoxicity as described in Section 7.1.1.
 - A laboratory value meeting any of the following criteria:
 - Absolute neutrophil count $<1.0 \times 10^3/\mu\text{L}$
 - Absolute lymphocyte count $<0.5 \times 10^3/\mu\text{L}$

A study participant may remain in the study if the result is transient. A retest is required within 1 to 2 weeks at a scheduled or unscheduled visit. If the repeat absolute neutrophil count or absolute lymphocyte count is still below the allowable values, the study participant must be withdrawn. If the repeat absolute neutrophil count or absolute lymphocyte count is above the allowable values, the study participant may continue in the study.

6. There is confirmation of a pregnancy during the study, as evidenced by a positive pregnancy test. See Section 10.4 (Appendix 4) for more information regarding pregnancies.
7. Study participant experiences a severe AE, an SAE, or a clinically significant change in a laboratory value that, in the opinion of the Investigator, merits the discontinuation of IMP and appropriate measures being taken.
8. Study participant considered as having either a suspected new LTBI or who develops an active TB or NTMB infection during the study must be immediately discontinued from IMP, and a PEOT Visit must be scheduled as soon as possible, but not later than the next regular visit.

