7.1.1 Potential drug-induced liver injury IMP discontinuation criteria

Study participants with potential drug-induced liver injury (PDILI) must be assessed to determine if IMP must be discontinued. In addition, all concomitant medications and herbal supplements that are not medically necessary should also be discontinued.

Immediate and permanent discontinuation of IMP is required for study participants with either of the following PDILI criteria:

- ALT or AST $\geq 8 \times \text{ULN}$
- ALT or AST $\geq 3 \times \text{ULN}$ and coexisting total bilirubin $\geq 2 \times \text{ULN}$

Immediate discontinuation of IMP is required for study participants with the following PDILI criterion:

- Study participants with ALT or AST $\geq 3 \times \text{ULN}$ who exhibit temporally associated symptoms of hepatitis or hypersensitivity. Hepatitis symptoms include fatigue, nausea, vomiting, and right upper quadrant pain or tenderness. Hypersensitivity symptoms may include fever (without clear alternative cause), rash, or eosinophilia.

If a nondrug-related cause for the symptoms can be confirmed, these study participants may resume IMP administration after discussion with the responsible UCB Study Physician, but only when the requirements for rechallenge with IMP (as provided in Section 10.6 [Appendix 6]) are met.

Study participants with the PDILI criterion below may be allowed to continue on IMP at the discretion of the Investigator:

- Study participants with ALT or AST $\geq 5 \times \text{ULN}$ and $< 8 \times \text{ULN}$, total bilirubin $< 2 \times \text{ULN}$, and no eosinophilia, with no fever, rash, or symptoms of hepatitis (eg, fatigue, nausea, vomiting, right upper quadrant pain or tenderness).

Evaluation of PDILI must be initiated (as described in Section 10.6 [Appendix 6]), with repeat tests performed in 2 weeks. Upon retest, if ALT or AST values have reduced to $< 5 \times \text{ULN}$, the study participant can continue with the study. However, if ALT or AST values remain $\geq 5 \times \text{ULN}$ and $< 8 \times \text{ULN}$ after retest, IMP should be temporarily withheld, and study participant should undergo a repeat test in 2 weeks. If ALT or AST values remain

$\geq 5 \times \text{ULN}$ even after the second retest, then the study participant should be permanently withdrawn from the study and should be followed for PDILI.

If a study participant is unable to comply with the applicable monitoring schedule, IMP must be discontinued immediately.

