ALT=alanine aminotransferase; AST=aspartate aminotransferase; BUN=blood urea nitrogen; eCRF=electronic Case Report Form; GGT=gamma glutamyltransferase; HBsAg=hepatitis B surface antigen; hCG=human chorionic gonadotropin; HIV=human immunodeficiency virus; IGRA=interferon-gamma release assay; INR=international normalized ratio; LDH=lactate dehydrogenase; MCH=mean corpuscular hemoglobin; MCHC=mean corpuscular hemoglobin concentration; MCV=mean corpuscular volume; RBC=red blood cell count; ULN=upper limit of normal; WBC=white blood cell count; WOCBP=woman of childbearing potential

^a Details of liver chemistry stopping criteria and required actions and follow-up assessments after liver stopping or monitoring event are provided in Section 7.1.1 and Appendix 6 (Section 10.6). All events of ALT $\geq 3 \times$ ULN and bilirubin $\geq 2 \times$ ULN ($>35\%$ direct bilirubin) or ALT $\geq 3 \times$ ULN and INR >1.5 , if INR measured, may indicate severe liver injury (potential Hy's Law) and must be reported as an SAE.

Investigators must document their review of each laboratory safety report.

Laboratory/analyte results that could unblind the study will not be reported to investigative sites or other blinded personnel until the study has been unblinded.

PUBLIC COPY

This document cannot be used to support any marketing authorization application and any extensions or variations thereof.

10.3 Appendix 3: Adverse events – Definitions and procedures for recording, evaluating, follow up, and reporting

Definition of AE

AE definition

 An AE is any untoward medical occurrence in a patient or clinical study participant, temporally associated with the use of IMP, whether or not considered related to the IMP. NOTE: An AE can therefore be any unfavorable and unintended sign (including an abnormal laboratory finding), symptom, or disease (new or exacerbated) temporally associated with the use of IMP.

Events meeting the AE definition

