When IMP is discontinued, all concomitant medications and herbal supplements that are not medically necessary should also be discontinued. In these cases, the Investigator should also consider dose reduction for medically necessary concomitant medication and consider changing any medically required concomitant medication known to be hepatotoxic to a suitable alternative.

When IMP is stopped due to PDILI (as described in Section 7.1.1), IMP must be permanently discontinued unless a subsequent alternative diagnosis fully explains the hepatic findings. If a subsequent alternative diagnosis fully explains the hepatic findings, and the requirements provided in Section 10.6.2.1 are met, rechallenge with IMP may be appropriate.

The approach to investigate PDILI is summarized in Table 10-3.

Table 10-3: Required investigations and follow up for PDILI

Laboratory value			Immediate		Follow up	
ALT or AST	Total bilirubin	Symptoms ^a of hepatitis or hypersensitivity	Consultation requirements	Actions	Testing	Evaluation
$\geq 3 \times \text{ULN}$	$\geq 2 \times \text{ULN}^b$	N/A	Hepatology consult ^c Medical Monitor must be notified within 24 hours (eg, by laboratory alert) and study participant discussed with Medical Monitor ASAP.	Immediate IMP discontinuation ^d	Essential: Must have repeat liver chemistry values and additional testing completed ASAP (see Section 10.6.3); recommended to occur at the site with HCP.	Monitoring of liver chemistry values at least twice per week until values normalize, stabilize, or return to within Baseline values. ^e
$\geq 3 \times \text{ULN}$	N/A	Yes				
$\geq 8 \times \text{ULN}$	N/A	N/A	Need for hepatology consult to be discussed (required if ALT or AST $\geq 8 \times \text{ULN}$) Medical Monitor must be notified within 24 hours (eg, by laboratory alert) and study participant discussed with Medical Monitor ASAP.			
$\geq 5 \times \text{ULN}$ (and $\geq 2 \times \text{Baseline}$) and $< 8 \times \text{ULN}$	$< 2 \times \text{ULN}$	No	Discussion with Medical Monitor required. Consider need for hepatology consult if there is no evidence of resolution (see	Further investigation – immediate IMP discontinuation not	Essential: Every attempt must be made to have repeat liver chemistry values and additional testing completed within 48 hours at the site with HCP (see Section 10.6.3).	Monitoring of liver chemistry values at least twice per week for 2 weeks. ^e 
• Immediate IMP discontinuation required if liver

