10.6.2.1 IMP restart/rechallenge

Study participants who are immediately discontinued from IMP due to having met certain criteria for PDILI (as described in Section 7.1.1 and Table 10-3), but for whom an alternative diagnosis is confirmed, ie, drug-induced liver injury is excluded, can rarely restart IMP.

Rechallenge with IMP can occur only if ALL of the following requirements are met:

- The results of additional testing and monitoring described in Section 10.6.3 and Section 7.1.1.1 confirm a nondrug-related cause for the abnormal hepatic laboratory parameters and any associated symptoms (ie, a subsequent alternative diagnosis fully explains the hepatic findings).
- No alternative treatment options are available to the study participant.
- The study participant has shown clear therapeutic benefit from the IMP.
- Study participant's ALT or AST elevations do not exceed $\geq 5 \times \text{ULN}$.
- Study participant's total bilirubin is $< 2 \times \text{ULN}$.
- Study participant has no signs or symptoms of hypersensitivity or hepatitis.
- The rechallenge is approved by the UCB Study Physician and a hepatologist. The hepatologist must be external to UCB. It is recommended that the hepatologist be a local hepatology expert or the hepatologist treating the study participant.
- Study participant agrees to the Investigator-recommended monitoring plan and understands his/her individual benefit/risk for restarting IMP and this is adequately documented.

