^a Tests in addition to the specified analytes may be performed based on the Investigator's medical judgment and study participant history.

^b Measured only for study participants with ALT $>8 \times \text{ULN}$, elevations in total bilirubin, and symptoms of hepatitis or hypersensitivity. Hepatitis symptoms include fatigue, nausea, vomiting, and right upper quadrant pain or tenderness; hypersensitivity symptoms include eosinophilia, rash, and fever (without clear alternative cause).

^c For WOCBP.

Table 10-5: PDILI information to be collected

New or updated information

 Concomitant prescriptions and over-the-counter medications (eg, acetaminophen, herbal remedies, vitamins); dosages and dates should be included.

 Pertinent medical history, including the following: 
 History of liver disease (eg, autoimmune hepatitis, nonalcoholic steatohepatitis, or other “fatty liver disease”) Adverse reactions to drugs Allergies Relevant family history or inheritable disorders (eg, Gilbert’s syndrome, alpha-1 antitrypsin deficiency) Recent travel Progression of malignancy involving the liver (Note: Metastatic disease to the liver, by itself, should not be used as an explanation for significant AST and/or ALT elevations.)

 The appearance or worsening of clinical symptoms of hepatitis or hypersensitivity (eg, fatigue, nausea, vomiting, right upper quadrant pain or tenderness, decreased appetite, abdominal pain, jaundice, fever, or rash)

 Recent clinically significant hypotension or hypoxemia with compromised cardiopulmonary function

 Alcohol and illicit drug use

 Results of liver imaging or liver biopsy, if done

 Results of any specialist or hepatology consult, if done

 Any postmortem/pathology reports

ALT=alanine aminotransferase; AST=aspartate aminotransferase; PDILI=potential drug-induced liver injury

10.7 Appendix 7: Medical device AEs, ADEs, SAEs, and device deficiencies: definition and procedures for recording, evaluating, follow up, and reporting

The definitions and procedures detailed in this appendix are in accordance with ISO 14155.

Both the Investigator and the Sponsor will comply with all local medical device reporting requirements.

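### Protocol Table 10-4 footnote b restricts INR testing to cases where ALT alone already stops treatment, and the rule allowing dosing to continue at 5 to <8×ULN ignores a measured INR

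*Protocol*

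**What the plan says.** Four places in the protocol bear on this.

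- **Appendix 2, Table 10-1 footnote a.** ALT ≥3×ULN with bilirubin ≥2×ULN (>35% direct), or ALT ≥3×ULN with INR >1.5 if INR was measured, "may indicate severe liver injury (potential Hy's Law) and must be reported as an SAE". The footnote sends the reader to 7.1.1 and Appendix 6 for stopping criteria and follow-up.
- **Section 10.6.3, Table 10-4 footnote b.** Prothrombin time/INR is in the list of tests for potential drug-induced liver injury, but it is "Measured only for study participants with ALT" above 8×ULN, "elevations in total bilirubin, and symptoms of hepatitis or hypersensitivity". Table 10-3 makes this work-up essential in the rows that stop IMP: "Must have repeat liver chemistry values and additional testing completed ASAP (see Section 10.6.3").
- **Section 7.1.1.** "Immediate and permanent discontinuation of IMP is required for study participants with either of the following PDILI criteria": ALT or AST ≥8×ULN, or ALT or AST ≥3×ULN with bilirubin ≥2×ULN. A third criterion, ALT or AST ≥3×ULN with symptoms, also stops IMP at once. Participants with ALT or AST 5 to <8×ULN, bilirubin <2×ULN and no symptoms "may be allowed to continue on IMP at the discretion of the Investigator".
- **Section 10.6.2.1.** "Rechallenge with IMP can occur only if ALL of the following requirements are met". Eight requirements follow, with limits for ALT/AST and bilirubin and none for INR.

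Section 8.3.6 defines potential Hy's Law, the only AE of special interest, as ALT or AST ≥3×ULN with bilirubin ≥2×ULN, without ALP ≥2×ULN and with no alternative explanation. It has no symptom condition and no INR condition.

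**The concern.** The protocol treats INR >1.5 alongside ALT ≥3×ULN as a possible sign of severe liver injury. Its testing rule asks for INR only in a corner where the result cannot alter the dosing decision, because ALT >8×ULN has already ended treatment. Between 3 and 8×ULN, where INR could separate a worrying case from a benign one, the work-up does not ask for it. If an investigator orders it anyway and finds it raised, the continuation rule for 5 to <8×ULN takes no account of it.

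What is at stake is the protection of a participant in an uncommon event. The efficacy analyses, the type I error rate and the sample size are not touched.

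**Working it through.** The documents give no figure to reproduce, so the check sets the rules side by side.

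**Step 1: when is INR guaranteed?** Footnote b lists three conditions: ALT >8×ULN, raised bilirubin (taken here as above ULN, since no cut-off is given) and symptoms. I compared each row of Table 10-3 with the literal reading (all three needed) and with a looser reading (any one is enough).

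| Table 10-3 row | All three needed | Any one enough |
|---|---|---|
| ALT or AST ≥3×ULN with bilirubin ≥2×ULN | No: ALT may be ≤8×ULN, AST alone may be raised, symptoms may be absent | Yes, through bilirubin |
| ALT or AST ≥3×ULN with symptoms | No: ALT may be ≤8×ULN, bilirubin may be normal | Yes, through symptoms |
| ALT or AST ≥8×ULN | No: bilirubin may be normal, symptoms may be absent | No: AST-only ≥8×ULN with normal bilirubin and no symptoms escapes |
| ALT or AST 5 to <8×ULN (and ≥2×Baseline), bilirubin <2×ULN, no symptoms | Never | No: escapes when bilirubin is normal |
| **Rows guaranteed** | **0 of 4** | **2 of 4** |

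Under the literal reading everyone sent for INR has ALT >8×ULN and so already meets the ≥8×ULN criterion for permanent discontinuation. Under the looser reading every 8.3.6 case is covered, because bilirubin ≥2×ULN is part of its definition.

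**Step 2: an 8.3.6 case.** Take ALT 6×ULN, bilirubin 2.5×ULN, normal ALP, no symptoms and no alternative explanation. This is an AE of special interest and IMP stops permanently (6 ≥3 and 2.5 ≥2). Under the literal footnote b, INR is not in the work-up (6 is not >8, and there are no symptoms).

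**Step 3: does a measured INR affect dosing?** Take ALT 6×ULN, bilirubin 1.2×ULN, no symptoms, and INR 1.7 drawn at the investigator's discretion.

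- Footnote a: 6 ≥3 and 1.7 >1.5, so it is an SAE.
- ALT or AST ≥8×ULN: not met.
- ALT or AST ≥3×ULN with bilirubin ≥2×ULN: not met, since 1.2 <2.
- ALT or AST ≥3×ULN with symptoms: not met.
- 7.1.1 continuation rule: met, since 5 ≤6 <8, bilirubin <2×ULN and no symptoms.

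The participant has an SAE labelled potential Hy's Law and may still be dosed under the liver rules. The stops in that row of Table 10-3 depend on compliance with monitoring, rising liver chemistry, or ALT/AST still ≥5×ULN on retest.

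**Step 4: count of rules naming INR.** Immediate-stop criteria in 7.1.1: 0 of 3. Rows of Table 10-3: 0 of 4. Rechallenge requirements in 10.6.2.1: 0 of 8, although the first of these reaches INR indirectly (see the objection).

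**The case against.** The best defence is that reporting and stopping are separate rules. Footnote a governs SAE reporting, and its condition that INR has been measured shows that INR was not meant as a routine trigger. That is fair: nothing in the documents says that every SAE criterion must stop treatment.

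The protocol also does more than its liver rules alone suggest:

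- Section 7.1 item 7 allows a stop for an SAE or a significant laboratory change that, "in the opinion of the Investigator, merits the discontinuation of IMP and appropriate measures being taken".
- Section 8 asks that immediate safety concerns go to the Sponsor at once, to settle whether IMP continues.
- Section 8.2.1 has clinically significant abnormal values repeated until they resolve, and Appendix 6 has abnormal hepatic values repeated.
- Appendix 3 obliges the investigator to arrange further tests that are medically indicated.
- The 5 to <8×ULN row requires discussion with the Medical Monitor and twice-weekly monitoring.

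These safeguards rule out two stronger readings. A reader might infer that a participant with ALT 4×ULN and INR 1.7 at Week 4, who fits no row of Table 10-3, would be dosed untested until the Week 16 panel. The repeat-test and Sponsor-discussion provisions do not allow that. A reader might also infer that rechallenge ignores INR. Its first requirement is that the 10.6.3 results confirm a non-drug cause that fully explains the hepatic findings, and PT/INR is among those tests. The Study Physician and an external hepatologist must also approve.

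Finally, footnote b may have been meant as a list of separate triggers, and Appendix 6 does say that tests depend on laboratory results and symptoms. That would cover the 8.3.6 cases. It would not cover the two patterns that escape in the table, nor give a measured INR any place in the continuation rule. What stands is that the specific rules are narrower than the general ones, and that sites are left to guess which reading of footnote b applies.

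**Conclusion.** The point holds and is minor. As written, footnote b guarantees INR in 0 of 4 Table 10-3 rows and leaves it out of potential Hy's Law cases with ALT 3 to 8×ULN, with AST-only elevation, or without symptoms. On the looser reading it covers 2 of 4 rows and all 8.3.6 cases. On either reading, 7.1.1 and Table 10-3 allow dosing at 5 to <8×ULN whatever a measured INR shows.

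The documents do not support a claim that participants would be left unmonitored, or that any efficacy result is affected. Permanent discontinuation at bilirubin ≥2×ULN with ALT or AST ≥3×ULN is unaffected, and SAEs and liver events remain 24-hour reports.

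The conclusion rests on taking footnote b as printed and on reading raised bilirubin as above ULN. The documents give no rate for INR >1.5 with bilirubin <2×ULN, no symptoms and transaminases below 8×ULN, so I put no number on how often the gap would matter. I assume that it would be rare among about 120 participants.

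**What to change.** 1. **Table 10-4 footnote b.** Reword so that PT/INR is measured in every Table 10-3 event: ALT or AST ≥3×ULN with bilirubin ≥2×ULN or with symptoms, ALT or AST ≥8×ULN, and the 5 to <8×ULN row. This settles whether the list is joint or alternative and brings in AST.
2. **Section 7.1.1 and Table 10-3, 5 to <8×ULN.** Allow IMP to continue only if INR is ≤1.5 or the INR elevation is explained by anticoagulant treatment. Otherwise withhold IMP pending Medical Monitor and hepatology review.
3. **Section 10.6.2.1.** Add the same INR condition to the rechallenge requirements.

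No existing SAE, AE of special interest or stopping trigger is removed. The cost is edits in four protocol places, one coagulation sample per liver work-up (a test already listed in Table 10-4), and an occasional extra interruption of IMP. The anticoagulant exception limits false triggers.

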10.4 Appendix 4: Contraceptive guidance and collection of pregnancy information

Definitions

Woman of childbearing potential (WOCBP): A woman is considered fertile following menarche and until becoming postmenopausal unless permanently sterile (see below).

Women in the following categories **are not considered WOCBP**:

1. Premenarchal
2. Premenopausal female with 1 of the following:
 - Documented hysterectomy
 - Documented bilateral salpingectomy
 - Documented bilateral oophorectomy

Note: Documentation can come from the site personnel's review of the study participant's medical records, medical examination, or medical history interview.

3. Postmenopausal female
 - A postmenopausal state is defined as no menses for 12 months without an alternative medical cause. A high follicle stimulating hormone (FSH) level in the postmenopausal range may be used to confirm a postmenopausal state in women not using hormonal contraception or hormonal replacement therapy (HRT). However, in the absence of 12 months of amenorrhea, a single FSH measurement is insufficient.
 - Females on HRT and whose menopausal status is in doubt will be required to use one of the nonestrogen hormonal highly effective contraception methods if they wish to continue their HRT during the study. Otherwise, they must discontinue HRT to allow confirmation of postmenopausal status before study enrollment.

Contraception guidance

Female study participants

Female study participants of childbearing potential are eligible to participate if they agree to use a highly effective method of contraception consistently and correctly as described in [Table 10-2](#).

Table 10-2: Highly effective contraceptive methods

Highly effective contraceptive methods that are user dependent^a
 
Failure rate of <1% per year when used consistently and correctly.

Combined (estrogen and progestogen containing) hormonal contraception associated with inhibition of ovulation
 
 • Oral • Intravaginal • Transdermal

Progestogen only hormonal contraception associated with inhibition of ovulation
 
 • Oral • Injectable

Highly effective methods that are user independent

Implantable progestogen-only hormonal contraception associated with inhibition of ovulation
 
 • IUD • IUS • Bilateral tubal occlusion

Vasectomized partner
 
A vasectomized partner is a highly effective contraception method provided that the partner is the sole male sexual partner of the WOCBP and the absence of sperm has been confirmed. If not, an additional highly effective method of contraception should be used.

Sexual abstinence
 
Sexual abstinence is considered a highly effective method only if defined as refraining from heterosexual intercourse during the entire period of risk associated with the IMP. The reliability of sexual abstinence needs to be evaluated in relation to the duration of the study and the preferred and usual lifestyle of the study participant.

IMP=investigational medicinal product; IUD=intrauterine device; IUS=intrauterine hormone-releasing system;
WOCBP=woman of childbearing potential

Note: In case of newly started contraception pills/IUDs, Investigator should consider the correct timing of starting/applying such methods in relation to the menstrual cycle and the manufacturing instruction as to when these newly started methods would become effective.

^a Typical use failure rates may differ from those when used consistently and correctly. Use should be consistent with local regulations regarding the use of contraceptive methods for study participants participating in clinical studies.

Pregnancy testing

- Woman of childbearing potential should only be included after a confirmed menstrual period and a negative highly sensitive serum pregnancy test.
- Additional pregnancy testing should be performed as indicated in the SoA (Table 1-1) and as required locally.
- Pregnancy testing will be performed whenever a menstrual cycle is missed or when pregnancy is otherwise suspected.

Male study participants with partners who become pregnant

- The Investigator will attempt to collect pregnancy information on any male study participant's female partner who becomes pregnant while the male study participant is in this study. This applies only to male study participants who receive bimekizumab. If the study participant is later found to be on placebo, then pregnancy data collection can stop.
- In cases where the partner of a male study participant enrolled in a clinical study becomes pregnant, the Investigator or designee is asked to contact the study participant to request consent of the partner via the Partner Pregnancy Consent Form that has been approved by the responsible IRB/IEC and should be available in the Investigator site file. In case of questions about the consent process, the Investigator may contact the UCB/CRO contract monitor for the study. The Investigator will complete the information in the eCRF only after the partner has agreed that additional information can be captured and has provided the signed Partner Pregnancy Consent Form. UCB's PS department is also the primary contact for any questions related to the data collection for the partner pregnancy, eventual birth, and follow up.
- After obtaining the necessary signed informed consent from the pregnant female partner (and/or parent/legal representative), the Investigator will record pregnancy information on the appropriate form and submit it to the Sponsor within 24 hours of receipt of the information. The female partner will also be followed to determine the outcome of the pregnancy. Information on the status of the mother and child will be forwarded to the Sponsor. Generally, the follow up will be ≥ 30 days after the delivery date. Any termination of the pregnancy will be reported regardless of fetal status (presence or absence of anomalies) or indication for the procedure.

Female study participants who become pregnant

- Any female study participant who becomes pregnant while participating in the study will discontinue IMP (see Section 8.3.5).
- The Investigator will collect pregnancy information on any female study participant who becomes pregnant while participating in this study. Information will be recorded on the appropriate form and submitted to the Sponsor within 24 hours of receipt of the information. The study participant will be followed to determine the outcome of the pregnancy. The Investigator will collect follow-up information on the study participant and the neonate, and the information will be forwarded to the Sponsor. Generally, the follow up will be ≥ 30 days after the delivery date. Any termination of pregnancy will be reported, regardless of fetal status (presence or absence of anomalies) or indication for the procedure.
- While pregnancy itself is not considered to be an AE or SAE, any pregnancy complication or elective termination of a pregnancy will be reported as an AE or SAE. A spontaneous abortion is always considered to be an SAE and will be reported as such. Any poststudy pregnancy-related SAE considered reasonably related to the IMP by the Investigator will be reported to the Sponsor as described in Section 8.3.5. While the Investigator is not obligated to actively seek this information in former study participants, he or she may learn of an SAE through spontaneous reporting.

